### Other Potential Toxicity/Events of Special Interest

Based on nonclinical findings in rats and dogs and based on clinical findings, increased cholesterol was identified as a laboratory abnormality of interest.

Renal complications are considered an event of special interest for JNJ-6379. Immediate treatment-emergent decrease in mean eGFR, which was initially observed in the JADE study, has also been observed in both JNJ-6379 treatment arms in the ongoing REEF-1 study. The eGFRcr values remained reduced during treatment, with a fast rebound after end of treatment. The eGFR decrease (calculated from serum creatinine) may be an anomaly due to JNJ-6379 possibly interfering with tubular excretion of creatinine via inhibition of MATE-1 transporter. This hypothesis was supported by the absence of a pattern of increased biomarkers of proximal tubulo-toxicity (the beta-2microglobulin/creatinine and the retinol binding protein/creatinine ratios), suggesting that the eGFRcr reduction was due to transporter inhibition at the level of creatinine excretion from the proximal tubule rather than renal toxicity.

Emerging data from the REEF-2 study became available, confirming the transient pattern of eGFRcr declines but, in addition, showing an increase of the beta-2microglobulin/creatinine and the retinol binding protein/creatinine ratios in some participants when TDF was continued and combined with JNJ-6379+JNJ-3989. These new data are suggesting that JNJ-6379 in combination with TDF may contribute to renal tubulo-toxicity.

Hematologic abnormalities are considered an event of special interest for JNJ-3989 and JNJ-6369. Mild thrombocytopenia was observed in recently conducted non-clinical toxicology studies with the combination of JNJ-3989 and JNJ-6379. In addition, in a 3-month combination study with 80 rats, 1 rat developed pancytopenia related to bone marrow depletion after 23 days of dosing. Previously, in a 9-month dog study in 24 dogs treated with JNJ-6379 alone, pancytopenia which correlated with a marked increase in plasma cell-like cells in the bone marrow was observed in 1 dog after 60 days of dosing. Refer to Section 8.5.6.5. A minor additive effect was observed in vitro in human bone marrow derived erythroid and myeloid progenitors when combining JNJ-6379 and Peg-IFN- $\alpha$ 2a.

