#### Study Intervention Administration

Study intervention administration must be captured in the source documents and the CRF.

JNJ-3989 injections will be administered SC (preferably in the abdomen) at the study site.

In between study visits, participants will take their oral study intervention (NA treatment) at home and they will bring their oral study intervention with them to each study visit. At study visits, the

oral study intervention should be taken on site to allow biochemistry and renal biomarker samples to be taken in fasted conditions.

During the study, virologically suppressed participants will continue the same NA treatment they were receiving at time of screening (and during at least 3 months prior to screening). In case participants experienced toxicity to ETV, tenofovir disoproxil, or TAF prior to screening, they should be treated with one of the other two NAs during this study.

Participants who are not receiving any HBV treatment at screening will receive tenofovir disoproxil at start of intervention.

If clinically indicated, switching from one NA treatment (ETV, tenofovir disoproxil, or TAF) to another NA treatment (ETV, tenofovir disoproxil, or TAF) during the study is allowed for all participants after consultation with the sponsor.

For PegIFN- $\alpha$ 2a, administration should be done SC in the thigh or abdomen, preferably in the evening by self-injection. Used PegIFN- $\alpha$ 2a syringes should be separated from the needle via the sharps container and then placed into their original box and returned to the site, if allowed per local guidelines and regulations. The used needles in the sharps container will be returned to the study site after completion of treatment with PegIFN-  $\alpha$ 2a or disposed of following local standard procedures. If desired, participants can also choose to have the weekly administration of PegIFN- $\alpha$ 2a performed at the study site irrespective of the time of day.

If JNJ-3989 and PegIFN- $\alpha$ 2a are both injected in the abdomen, they should be injected into different areas of the abdomen and approximate location should be recorded.

For a definition of study intervention overdose, refer to Section 8.5.7.

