Calcium (Ionized), High (mg/dL; mmol/L)	>ULN to <6.0 >ULN to <1.5	6.0 to <6.4 1.5 to <1.6	6.4 to <7.2 1.6 to <1.8	≥7.2 ≥1.8
Calcium, Low (mg/dL; mmol/L) aged ≥7 days	7.8 to <8.4 1.95 to <2.10	7.0 to <7.8 1.75 to <1.95	6.1 to <7.0 1.53 to <1.75	<6.1 <1.53
	aged <7 days	6.5 to <7.5 1.63 to <1.88	6.0 to <6.5 1.50 to <1.63	5.50 to <6.0 1.38 to <1.50
Calcium (Ionized), Low (mg/dL; mmol/L)	<LLN to 4.0 <LLN to 1.0	3.6 to <4.0 0.9 to <1.0	3.2 to <3.6 0.8 to <0.9	≤3.2 ≤0.8
Cardiac Troponin I, High	NAP	NAP	NAP	Levels consistent with myocardial infarction or unstable angina as defined by the local laboratory
Creatine Kinase, High	3 to <6×ULN	6 to <10×ULN	10 to <20×ULN	≥20×ULN
Creatinine, High Report only IP	1.1 to 1.3×ULN	>1.3 to 1.8×ULN OR Increase to 1.3 to <1.5×participant's baseline	>1.8 to <3.5×ULN OR Increase to 1.5 to <2.0×participant's baseline	≥3.5×ULN OR Increase of ≥2.0×participant's baseline
Creatinine Clearanceq or eGFR, Low Report only IP	NAP	<90 to 60 ml/min or ml/min/1.73 m  OR 10% to <30% decrease from participant's baseline	<60 to 30 ml/min or ml/min/1.73 m  OR 30% to <50% decrease from participant's baseline	<30 ml/min or ml/min/1.73 m  OR ≥50% decrease from participant's baseline or dialysis needed
Glucose (mg/dL; mmol/L) Fasting, High	110 to 125 6.11 to <6.95	>125 to 250 6.95 to <13.89	>250 to 500 13.89 to <27.75	>500 ≥27.75
	Nonfasting, High	116 to 160 6.44 to <8.89	>160 to 250 8.89 to <13.89	>250 to 500 13.89 to <27.75
Glucose, Low (mg/dL; mmol/L) aged ≥1 month	55 to 64 3.05 to <3.55	40 to <55 2.22 to <3.05	30 to <40 1.67 to <2.22	<30 <1.67
	aged <1 month	50 to 54 2.78 to <3.00	40 to <50 2.22 to <2.78	30 to <40 1.67 to <2.22
Lactate, High	ULN to <2.0×ULN without acidosis	≥2.0×ULN without acidosis	Increased lactate with pH <7.3 without life threatening consequences	Increased lactate with pH <7.3 with life threatening consequences

eGFR: estimated glomerular filtration rate; LLN: lower limit of normal; NAP: not applicable; ULN: upper limit of normal

p Reminder: Choose the method that selects for the higher grade.

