5.6. Safety Analyses

All safety analyses will be based on the safety analysis set based on actual study intervention received, unless otherwise specified. Summaries will be provided on the overall population and by study panel and analysis phase unless specified otherwise.

For all continuous safety variables, descriptive statistics will include the N, mean, standard deviation, median, minimum, and maximum. Categorical variables will be summarized using frequency counts and percentages.

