Abnormality criteria ([based on the criteria specified in the DAIDS Toxicity Grading Scale (see Clinical Protocol Appendix 8, DAIDS Table)]) will be applied to baseline and postbaseline values or in accordance with the normal ranges of the clinical laboratory if no gradings are available.

Postbaseline abnormalities will be compared with their corresponding baseline result:

- For toxicity grades, treatment emergent (TE) will be concluded if the postbaseline grade is worse than the baseline grade.
- For abnormalities based on normal range and/or criteria: If the postbaseline value is above the upper limit and the baseline value is below the upper limit (e.g., Normal or Low), then the postbaseline abnormality will be considered TE. The same applies to the postbaseline value being below the lower limit with the baseline value being above the lower limit (e.g., Normal or High).
- If the baseline value is missing, a postbaseline abnormality will always be considered as TE.

For each lab parameter, a worst-case analysis will be performed by using the worst abnormality and/or worst toxicity grade lab value and time point per participant ([Appendix 9](#)). The worst toxicity case is the value associated to the highest toxicity grade and is derived per parameter and

toxicity direction (hypo / hyper). Worst-case will be derived within each phase, including unscheduled assessments. For abnormalities, in case the same subject has both abnormalities (low and high) for the same lab test within the same phase, the participant will be counted in the analysis for both toxicity directions (abnormally high and low).

Imputation rules:

In case continuous laboratory results are not numerically expressed, but as a character (e.g., 'less than 2', '>25'), these results will be numerically imputed as follows:

- If the analysis result contains '<' then the result will be multiplied by 0.999 (e.g., <6.1 becomes 6.0939).
- If analysis result contains '>' then the result will be multiplied by 1.001 (e.g., >6.1 becomes 6.1061).
- If analysis result contains ' \leq ' or ' \geq ' then only the numeric portion of the result will be used.

This also applies to normal limits expressed as such.

Shift tables will be provided summarizing the shift in laboratory values from baseline over time with respect to abnormality criteria (low, normal, high) for each laboratory parameter by study phase.

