5.6.3.1.1. Creatinine and Glomerular Filtration

Creatinine and glomerular filtration analyses will be analysed over time.

5.6.3.1.1.1. eGFR

Stages of eGFR (eGFRcr or eGFRcys, as described in [Table 5](#)) at baseline versus the minimum corresponding post-baseline eGFR value and the last available value will be summarized by count and percent of participants. Stage of chronic kidney disease (CKD) are defined as follows: 1 (Normal): eGFR ≥ 90 ; 2 (Mild): eGFR 60-89; 3 (Moderate): eGFR 30-59; 4 (Severe): eGFR <30 .

In addition to the above, the number and proportion of participants with a $<10\%$, $10-30\%$, $30-50\%$ and $\geq 50\%$ decrease from baseline will be tabulated.

Scatter plots of eGFR (eGFRcr or eGFRcys) versus other renal biomarkers (total urine protein, total urine albumin, urine protein to creatinine ratio [UPCR], urine albumin to creatinine ratio [UACR], retinol binding protein (RBP) and beta-2-microglobulin, RBP to creatinine ratio and beta-2-microglobulin to creatinine ratio, and urine fractional excretion of phosphate [FEPO4]) will also be presented.

5.6.3.1.1.2. Proximal Renal Tubular Function

Proteinuria by Quantitative Assessment

Total urine protein, total urine albumin, UPCR and UACR will be summarized by study panel and visit using descriptive statistics.

The number and proportion of participants with UACR and UPCR results in the following categories over time will be tabulated:

- UACR: < 30 , ≥ 30 to 300 , >300 mg/g
- UPCR: < 200 mg/g versus ≥ 200 mg/g

Median (Q1, Q3) percent change from baseline over time will be plotted by study panel.

The evolution over time of total urine protein and total urine albumin will also be presented.

Proteinuria by Urinalysis (Dipstick)

Treatment-emergent proteinuria by urinalysis (dipstick) over time will be summarized by study panel. Cross-tabulation of grades overtime versus baseline will also be presented.

Other Renal Biomarkers

Selected renal biomarkers RBP and beta-2-microglobulin, RBP to creatinine ratio and beta-2-microglobulin to creatinine ratio will be summarized by study panel and visit using descriptive statistics.

The proportions of participants with beta-2-microglobulin to creatinine ratio ≤ 343.5 $\mu\text{g/g}$ and >343.5 $\mu\text{g/g}$ will be tabulated.

The number and proportion of participants with RBP to creatinine ratio results in the following categories overtime will be tabulated:

- < 50 years of age: < 130 mcg/g creatinine, \geq 130 mcg/g creatinine

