5.7.4. Definition of Subgroups

Table 6: List of Subgroups of Interest for Efficacy and/or Safety Purpose

Subgroup	Purpose	Definition
Sex	Efficacy, Safety	Male, Female
Age Group	Efficacy, Safety	≤ 45 years, > 45 years
Race	Efficacy, Safety	Asian, Non-Asian
Body Mass Index	Safety	≤ 25 , $>= 25$
HBsAg level at baseline	Efficacy	<1000 vs. $>=1000$ $<10,000$ vs. $>=10,000$
Type of NA at Study Entry	Safety	TD, TAF
Received PegIFN- α 2a (Optional)	Efficacy, Safety	Yes/No
HBsAg % Positive Cells	Efficacy	$<$ Median vs. $>=$ Median Value

This list of subgroups may be modified based on interim/final results and clinical interest.

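### No planned safety summary is split by JNJ-6379 exposure, so the Panel 1, Panel 2 and pooled renal, cholesterol and worst-laboratory tables mix exposed and unexposed participants

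*SAP*

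**What the plan says.** SAP 5.6 gives the default for every safety output: "Summaries will be provided on the overall population and by study panel and analysis phase unless specified otherwise". The sections on laboratory tests, eGFR, proximal tubular markers and phosphate excretion (SAP 5.6.3.1 onward) keep to panel, visit and phase.

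SAP Table 6 (5.7.4) lists the subgroups with a safety purpose: sex, age, race, BMI, type of NA at entry, and PegIFN-α2a. JNJ-6379 is absent. A closing note adds: "This list of subgroups may be modified based on interim/final results and clinical interest". SAP 5.6.3.1 stratifies the worst-toxicity table by these subgroups and no others.

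A yes/no flag for at least one dose of JNJ-6379 does exist, in SAP 5.3.1.3, as an optional exploration of the primary efficacy endpoint. SAP 5.4.3 extends it, again optionally, to key secondary endpoints.

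Two rules fix what the renal and laboratory tables retain. For laboratory worst cases: "Worst-case will be derived within each phase, including unscheduled assessments". For eGFR stage, baseline is set "versus the minimum corresponding post-baseline eGFR value and the last available value will be summarized by count and percent of participants".

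The notes to Figure 2 in both documents say that former Arm 1 participants are analysed as part of Arm 2. SAP 1.2 says that Panel 3 enrolled nobody before Amendment 5, so it has no JNJ-6379 exposure.

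**The concern.** The protocol itself treats JNJ-6379 exposure as a safety distinction. Section 8.5.6 says that renal complications and cholesterol increase are of special interest because of JNJ-6379. It keeps them on the list because earlier participants took the drug, and continues renal monitoring for anyone who had at least one dose. Sections 2.3.2.2.2 and 4.2 give the renal profile as part of the reason for withdrawing the drug.

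So the protocol identifies the exposed group for monitoring, but no SAP summary table shows that group. A reader who wants the renal and cholesterol profile of JNJ-3989 + NA, the regimen now under study, cannot get it from the planned tables for Panels 1 and 2. A low eGFR or raised cholesterol count there could come from the remaining regimen or from the withdrawn drug.

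**Working it through.** The SAP gives no figure to reproduce. The check is whether any planned safety summary separates the groups, and where the mixing would show.

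**1. Search for a split.**
- SAP 5.6.1: exposure and duration by agent. This describes JNJ-6379 use, not outcomes.
- SAP 5.6.2: AEs by relationship to each agent, and AEs leading to discontinuation of each agent. These follow the investigator's attribution or a stopping decision, not exposure. AESI incidence has no exposure split.
- SAP 5.6.3.1 to 5.6.3.3: panel, visit and phase. Only the worst-toxicity table adds Table 6 subgroups, and JNJ-6379 is not among them.
- SAP 4: the Safety set is analysed by intervention actually received, but no display by intervention follows, and the Figure 2 note pools the arms.
- SAP 5.4.3: optional, limited to undefined key secondary endpoints, and placed in a section run on the ITT set.

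No planned safety summary is by exposure.

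**2. Where mixing can show.** Protocol 2.3.2.2.2 says of JNJ-6379: "The eGFRcr values remained reduced during treatment, with a fast rebound after end of treatment". Set beside the SAP rules:
- *Worst-case laboratory tables.* The worst value in the open-label phase can date from time on JNJ-6379 and stays in the table after recovery.
- *eGFR stage, minimum value.* The same applies. The threshold is also low: in the DAIDS table (Protocol Appendix 9), a "10% to <30% decrease from" baseline is already grade 2, the lowest grade on that row.
- *eGFR stage, last available value.* Less affected, because a fall that has reversed would no longer show.
- *Open-label by-visit tables.* Affected for as long as exposed participants were taking the drug. The documents give no durations.

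For the beta-2-microglobulin and retinol binding protein to creatinine ratios, the same section reports raised "ratios in some participants when TDF was continued and combined with JNJ-6379+JNJ-3989", and states no rebound for those markers. Protocol 6.1 says: "Participants who are not receiving any HBV treatment at screening will receive tenofovir disoproxil at start of intervention". Exposed Panel 1 participants therefore received tenofovir disoproxil with JNJ-6379 unless their NA was switched. Panel 2 participants already on tenofovir disoproxil continued it.

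**3. Size.** For a panel of n with k exposed, and event rates p1 (exposed) and p0 (unexposed):

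panel rate = p0 + (k/n)(p1 − p0)

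The documents give none of k, p1 or p0, so the distortion cannot be calculated. What can be stated is the weight of one participant, using the enrolment range in SAP 3 (8 to 12 per panel, 18 to 24 in total):
- Panel: 1/12 = 8.3 points; 1/8 = 12.5 points.
- Panels 1 and 2: 1/24 = 4.2 points; 1/18 = 5.6 points.

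**4. Precision of a split.** The exact two-sided 80% upper limit for zero events is 1 − 0.1^(1/n): 17.5% for n = 12, 31.9% for n = 6 and 53.6% for n = 3. The group sizes are assumed. The result argues against splitting within a panel.

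**The case against.** The study is exploratory and single-arm since Amendment 5. The pooling of former Arm 1 is stated openly, and SAP Amendment 1 removed subgroups because the sample is small. Table 6 may be modified. With about 24 participants, listings may do the job: SAP 5.2 lists those who stop study treatment early, with panel, date and reason, and SAP 1.2 counts JNJ-6379 as study treatment. SAP 5.6.3.1 lists participants with a treatment-emergent laboratory abnormality.

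Much of this stands. The listings allow a determined reader to reconstruct exposure, and the attribution and discontinuation tables are safety summaries specific to JNJ-6379. It would be wrong to infer that the SAP has none. They still do not show outcomes by exposure, and a split added after seeing results is weaker than one fixed beforehand.

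Four stronger readings are tempting but unsupported:
- *The problem lies mainly in worst-case and minimum-value tables.* The documents do not say so. Without JNJ-6379 durations, by-visit tables cannot be ruled out.
- *The tenofovir trough difference in Protocol 2.2.2.2 measures the harm.* It is a pharmacokinetic comparison from another study and says nothing about distortion of these tables.
- *Half of each panel was exposed.* The target of 12 for Arm 1 belongs to the two-arm design. The number randomised before Amendment 5 is not given.
- *The SAP departs from the protocol without declaring it, because Protocol 9.4.2 still tabulates worst laboratory abnormalities by intervention arm while SAP Appendix 2 declares no change.* That wording is probably left over from the two-arm design. Aligning it with the pooling note is editorial.

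**Conclusion.** The point holds as a gap in layout. Followed as written, the SAP gives no safety summary by JNJ-6379 exposure, and the Panel 1, Panel 2 and pooled tables of AESIs, worst laboratory toxicity, eGFR, renal biomarkers and cholesterol mix the two groups. Panel 3 alone is unaffected.

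A reversed eGFR fall can remain in the open-label worst-case and minimum-value tables. Open-label by-visit tables can be affected too, and the last-value column less so. This rests on the protocol's account of JNJ-6379 in other studies and on some participants here having received it. How many did, and for how long, is not stated, so the size of the mixing is unknown.

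This is worth changing because the change is cheap and the protocol already treats the exposure as relevant. It does not threaten the primary endpoint or the study's conclusions.

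**What to change.** Add the SAP 5.3.1.3 flag (at least one dose of JNJ-6379, no/yes) to Table 6 with purpose Safety. Apply it descriptively to renal and cholesterol AESIs, worst laboratory toxicity, eGFR and renal biomarkers, for Panels 1 and 2 combined.

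The combined split does not by itself separate regimens within Panel 1, and it mixes NA types. Pair it with a listing of exposed participants giving panel, NA type, JNJ-6379 duration, and whether each abnormality arose before or after JNJ-6379 was stopped.

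Cost: one Table 6 row, which carries through to the worst-toxicity table under SAP 5.6.3.1; one further column in the AESI, eGFR and renal-biomarker tables; and one derived before/after flag based on the last JNJ-6379 date already used in SAP 5.6.1. The downside is small cells and a comparison that is not randomised, since enrolment after Amendment 5 was not. The SAP should say that no inference will be drawn from it.

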5.6.1. Extent of Exposure

The number and percentage of participants who receive each study treatment within a study panel will be summarized.

Descriptive statistics for duration (N, mean, SD, median, and range [minimum, maximum]) of JNJ-3989, JNJ-6379, and NA during the open-label phase, and of PegIFN- α 2a, will be summarized. Duration of treatment with NA will also be summarized for the follow up phase.

Because of the different route and frequency of treatment administration across the 3 agents (for JNJ-3989 one subcutaneous injection once every 4 weeks, for JNJ-6379 and for NA once daily tablet, and for PegIFN- α 2a one subcutaneous injection every week) the total duration of exposure (weeks) will be calculated for each study treatment as follows:

- JNJ-3989: $[\text{Min}((\text{Date of last injection} + 27 \text{ days}), \text{Date of trial disposition, cut-off date}) - \text{date of first injection} + 1] / 7$

- JNJ-6379: [Min (Date of the last JNJ-6379, Date of treatment disposition for JNJ-6379, Date of trial disposition, Date of clinical cut-off)- first drug administration date + 1] / 7
- NA: [Min (Date of the last NA administration in the given phase, Date of discontinuation from NA, Date of trial disposition, Date of clinical cut-off) - first drug administration date in the given phase + 1] / 7
- PegIFN- α 2a: [Min (Date of the last PegIFN- α 2a administration +6 days, Date of discontinuation from PegIFN- α 2a, Date of trial disposition, Date of clinical cut-off date) – Date of the first PegIFN- α 2a administration + 1] / 7

For NA treatment, the total duration of exposure will be calculated separately for the open-label and FU phases. For FU, the total duration will add up the weeks of NA treatment in the FU phase for those participants who did not stop NA prior to/at Week 48 and the NA re-treatment weeks, if any required. Those participants who stopped NA treatment at or before Week 48 and never restarted NA treatment thereafter will be counted as having zero weeks of NA exposure during the FU.

Cutoff dates will be defined to match the prespecified timepoints for interim analyses and the primary analysis, respectively (see Section 5.8).

The number and percentage of participants who skipped any dose of JNJ-3989 or NA during the open-label phase, or any dose of PegIFN- α 2a, will be summarized separately by study panel. Additionally, the number and percentage of participants who missed 2 or more JNJ-3989 injections, or who missed more than 5 doses of NA within a four week period will be provided as well as the distribution of the total number of JNJ-3989 injections received.

Study intervention compliance will be summarized descriptively. See [Appendix 7](#) Intervention Compliance for further details.

